The best overall response is the best response recorded from the start of the treatment on Cycle 1 Day 1 until disease progression/recurrence (taking as reference for progressive disease the smallest measurements recorded since the treatment started). If patients remain on treatment with partial response or stable disease past 6 months from the date of Cycle 1 Day 1, the first 6 months of treatment will be used to evaluate the primary endpoint of best overall response. In general, the patient's best response assignment will depend on the achievement of both measurement and confirmation criteria.

Target Lesions	Non-target Lesions	New Lesions	Overall Response
CR	CR	No	CR
CR	Non-CR/Non-PD	No	PR
PR	Non-PD	No	PR
SD	Non-PD	No	SD
PD	Any	Yes or No	PD
Any	PD	Yes or No	PD
Any	Any	Yes	PD

Patients with a global deterioration of health status requiring discontinuation of treatment without objective evidence of disease progression at that time should be reported as "symptomatic deterioration." Every effort should be made to document the objective progression even after discontinuation of treatment.

Conditions that may define early death include patients that have died without documentation of disease progression and before it was time to conduct the first tumor reassessment. Inevaluable patients include those who have received protocol treatment but did not have any follow-up assessment completed before initiation of alternative treatment.

In some circumstances, it may be difficult to distinguish residual disease from normal tissue. When the evaluation of complete response depends upon this determination, it is recommended that the residual lesion be investigated (fine needle aspirate/biopsy) before confirming the complete response status.

Guidelines for Evaluation of Measurable Disease

All patients in this study will be getting a baseline CT scan to include the target lesion (Table 3).

Confirmation Measurement/Duration of Response or Duration of Stable Disease

In patients who are confirmed to have CR/PR, the duration of overall response is measured from the time measurement criteria are met for CR/PR (whichever is first recorded) until the first date that recurrent or progressive disease is objectively documented (taking as reference for progressive disease the smallest measurements recorded since the treatment started).

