13.1 CRITERIA FOR REMOVAL FROM STUDY

Study treatments will be discontinued for all patients in the following situations:

- Disease progression
- General or specific changes in the patient's condition render the patient unacceptable for further treatment in the judgment of the investigator
- Unacceptable adverse event(s)
- Inability of patient to comply with study requirements

In addition to the above, patients may withdraw from the study at any time for any reason. Once decision has been made to stop study drug treatment, the treating physician will report on the date of last treatment and the reason for cessation of study drug treatments. Patients who are no longer receiving study drugs will still be followed clinically for toxicity and survival endpoints, unless the patient explicitly declines.

Procedures for Study Withdrawal

Withdrawal procedures will include an end-of-treatment (EOT) visit within 30 days of the last dose of study drug.

Replacement of Patients

During both Phase I and II of the study (dose-escalation), any patient who discontinues treatment before completing the first cycle of treatment (C1D21) will be considered not evaluable for DLT and will be replaced. Completion of the first cycle of treatment is defined by completion of at least 75% of both study drugs during the initial 28-Day DLT evaluation window (7-day safety run-in + 21-day Cycle 1). The only exception are patients who are unable to complete at least 75% of the prescribed dose of DS-3201b and irinotecan during the DLT evaluation period (safety run-in + Cycle 1) due to non-disease-related \geq Grade 2 adverse events; these patients will be considered to have a DLT and will not be replaced. Please see Section 11.0 for the full definition of DLTs.

During Phase II of the study, any patient who discontinues treatment before completing two cycles of treatment but has completed the DLT evaluation period will still undergo the first repeat CT scan prior to their scheduled C3D1. If a CT scan evaluation is unable to be obtained, these patients will not be replaced, and they will be considered as not deriving clinical benefit from the study drug.

Re-screening of Patients

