Adverse events will be graded according to the CTCAE version 5.0, with patients being assessed weekly while on the treatment. Data on pharmacokinetics (PK) of DS-3201b after DS-3201b administered alone or in combination with irinotecan will be collected 7 Days prior to C1D1, on C1D1, on C1D8, on C1D15 and on C2D15 for each patient in the phase I component of this study. Standard plasma PK parameters for each of the above timepoints will include the maximum plasma concentration (Cmax), minimum plasma concentration (Cmin), and time to maximum plasma concentration (Tmax). The area under the plasma concentration versus time curve (AUC) for DS-3201b will be estimated using non-compartmental analysis and/or a population PK approach.

Phase II:

The second phase of this study will be an open-label, single arm, phase II study of DS-3201b at the established RP2D in combination with fixed dose irinotecan. The primary objective of this study is to assess efficacy, ORR defined as CR+PR measured by RECIST v1.1.

Historical control:

We base the sample size calculation on the estimated response rate of 16% as a benchmark, which we derive from the reported study from Le Chevalier et al.³⁰ A two-stage Simon's minimax design will be employed to test the null hypothesis that the true ORR is 16% versus the alternative hypothesis that the true ORR is at least 35% with a type I error of 0.05 and a power of 0.8. In the first stage, 16 patients will be accrued. The first 6 patients out of this initial 16-patient cohort will be the 6 patients treated at MTD in Phase I.

Efficacy will be measured by RECIST v1.1 assessed response to therapy. If there are 2 or fewer responses in these 16 patients, the study will be stopped early for futility. The probability of stopping the study early for futility is 52% per the two-stage Simon's minimax design. If at least 3 patients show response in this first stage, we will request permission from the sponsor to enroll an additional 15 patients in the second stage. At the end of the study, if ≥ 9 patients out of total of 31 enrolled patients show a partial response or a complete response, then further investigation of DS-3201b in combination with irinotecan will be considered worthwhile.

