Study enrollment of the 17th patient will be suspended until the determination of the first-stage results, unless the benchmark of 3 patients with radiographic response is achieved by then. All patients will be included in the primary analysis, even if there are major protocol deviations. Patients are considered non-responses (PD) if they are not evaluable (including if CT scan evaluation not available) or died during the study. This study requires accrual of a minimum of 16 patients and up to a maximum of 31 patients if the cohort is expanded to the second stage. The accrual time is estimated to be between 10-24 months at the rate of 3 patients per month and a likely planned 4 months suspension between the first and second stages of this Phase II study.

To protect patients from excessive toxicity, a stopping rule for toxicity will be implemented during Phase II. Since the 6 patients treated at RP2D in Phase I will be included in the Phase II portion of the study, the early stopping rule for toxicity is calculated based on 31-

6=25 newly recruited patients. This toxicity rule will apply for the entire duration of the Phase II portion of the study.

Stopping rule:

Number of recruited patients	5	10	15	20	25
Number of DLT to stop the trial	≥2	≥3	≥3	≥3	≥4

Operating characteristics of the stopping rule:

True DLT rate	0.05	0.09	0.13	0.17	0.21	0.25
Probability of stopping the trial	0.09	0.30	0.54	0.74	0.87	0.94

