The ORR is defined as the proportion of patients with CR, or PR at any reassessment after start based on RECIST v1.1 criterion. The time frame for evaluating the primary endpoint of ORR for this portion of the study will be 6 months from the date of Cycle 1 Day 1 for each patient. The ORR and corresponding exact 95% CI will be reported. Progression-free survival will be measured from the start of treatment until the documentation of disease progression or death due to any cause, whichever occurs first, and censored on the date of last tumor assessment. In addition, we will document absence of tumor progression for patients who are still alive prior to data cutoff, dropout, or the initiation of alternate anticancer treatment. Overall survival will be determined as the time from the start of DS-3201b treatment to death, and censored on the last follow-up date. PFS and OS will be evaluated using the Kaplan-Meier method. The duration of response (for those with CR or PR) and durable of stable disease while on treatment (for those with SD) will also be evaluated using the Kaplan-Meier method.

All recorded toxicity data and adverse events of DS-3201b will be listed and tabulated by system organ class, preferred term and treatment. Any significant vital signs and clinical laboratory test results will be listed and summarized. Any significant physical examination findings and clinical laboratory results will be listed.

As secondary objectives, we will explore downstream mechanistic biomarkers of DS-3201b including SLFN11 expression and H3k27me3 signature by descriptive and graphical summaries of assays performed on tissue samples obtained during the study. The Wilcoxon rank sum test will be used to assess SLFN11 expression by immunohistochemistry as a potential predictive biomarker of response to DS-3201b and to correlate with trimethylation of H3K27 as measured by immunohistochemistry in pretreatment, on-treatment and post-treatment tissue samples as well as in circulating tumor cells (CTCs). In addition, next-generation sequencing (NGS) will also be performed on pre-treatment, on-treatment and post-treatment tissue samples obtained from the study. This data will be analyzed using descriptive

and graphic summaries of the assays performed, including use of gene expression heat maps and advanced computational biostatistics with collaborators in the [name] laboratory.

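### The Phase II non-response rule counts any death during the study as PD, with no exception for a CR or PR already documented

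*Combined protocol and SAP*

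**What the plan says.** Section 14.0 (Biostatistics, Phase II) keeps all patients in the primary analysis and then sets the coding rule: "Patients are considered non-responses (PD) if they are not evaluable (including if CT scan evaluation not available) or died during the study". The conditions are joined by *or*, so death is sufficient by itself. The sentence has no time limit, does not define *the study*, and does not mention responses already seen.

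Three other statements describe who counts as a responder:

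- Section 14.0 defines the ORR as the "proportion of patients with CR, or PR at any reassessment after start", with a time frame of "6 months from the date of Cycle 1 Day 1 for each patient".
- The final decision rule in Section 14.0 asks whether at least 9 of the "31 enrolled patients show a partial response or a complete response".
- Section 12.0 says: "The best overall response is the best response recorded from the start of the treatment on Cycle 1 Day 1 until disease progression/recurrence". It adds that, in general, the "best response assignment will depend on the achievement of both measurement and confirmation criteria".

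Neither section says which statement prevails when they disagree.

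**The concern.** The coding sentence decides who counts toward the stage 1 threshold (3 of 16) and the final threshold (9 of 31). A patient with a documented response who then dies is a responder under the three definitions and PD under the coding sentence.

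Followed exactly, the sentence removes true responders from the ORR and can lead to an active regimen being dropped. Left unresolved, it allows a choice between two counts after the data are known, in an open-label, single-arm trial. It also leaves unclear which patients enter the duration-of-response analysis, which Section 14.0 defines for those with CR or PR.

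**Working it through.** **1. One patient under each rule.** Scans are due every two cycles, about every six weeks (Table 3.0). Take a patient with PR at weeks 6 and 12 and no progression, who dies in month 4. The repeat scan keeps the confirmation question out of the example.

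- ORR definition, Section 14.0: responder, since PR was seen at a reassessment inside six months.
- Final decision rule, Section 14.0: counted toward the 9.
- Best overall response, Section 12.0: PR.
- Coding sentence, Section 14.0: non-response, PD.

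Reading the six-month window into the coding sentence does not resolve this, because the death falls inside the window.

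**2. The plan's design, reproduced.** Inputs from Section 14.0: null ORR 0.16, alternative 0.35; 16 patients in stage 1, continue with at least 3 responses; 31 in total, success with at least 9. With X1 ~ Bin(16, p) and X2 ~ Bin(15, p):

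- P(early stop) = P(X1 ≤ 2)
- P(success) = Σ over x = 3 to 16 of P(X1 = x) × P(X2 ≥ 9 − x)

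At p = 0.16: early stop 0.516 (plan: 52%), type I error 0.0474 (plan: 0.05). At p = 0.35: early stop 0.045, power 0.8009 (plan: 0.8). The design arithmetic is sound and holds if documented responses stand.

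**3. The coding sentence taken literally.** Let d be the share of true responders recoded because of a later death, assumed equal and independent across responders. The documents give no value, so d is shown as a range. With recoding at both stages, the counted response rate is p(1 − d), for example 0.35 × 0.90 = 0.315, and the formulas in step 2 apply. With recoding only at the final analysis, stage 1 uses true responders, and the final count given T true responders is Bin(T, 1 − d), needing at least 9.

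| d | Counted rate (true 0.35) | Power, both stages | Power, final only | Counted rate (true 0.16) | Type I error, both stages |
|---|---|---|---|---|---|
| 0 | 0.350 | 0.801 | 0.801 | 0.160 | 0.047 |
| 5% | 0.3325 | 0.740 | 0.743 | 0.152 | 0.036 |
| 10% | 0.315 | 0.670 | 0.675 | 0.144 | 0.026 |
| 20% | 0.280 | 0.507 | 0.514 | 0.128 | 0.013 |

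**4. A single recoded responder.** Each one lowers the reported ORR by 1/31 = 3.2 points. A result of 9/31 = 29.0% (exact 95% CI 14.2 to 48.0) meets the success rule; 8/31 = 25.8% (11.9 to 44.6) does not. At a true ORR of 35%, the chance of passing stage 1 and finishing on exactly 9 is 0.116. That is how often the result would be exposed to one such recoding at the final analysis. It is not the chance that the recoding happens, and it is not a power loss.

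**The case against.** *The intent is clear from context.* The sentence pairs death with being not evaluable. Section 12.0 describes early death as patients who "died without documentation of disease progression and before it was time to conduct the first tumor reassessment". Section 13.1 has a parallel rule under which certain patients without a CT evaluation are taken to have had no clinical benefit. On this view the sentence only handles missing outcomes. That is probably what was meant, and it stands as a reading of intent. But Section 14.0 neither uses nor cites the early-death category, and its wording is wider.

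*The endpoint is already limited to six months.* This answers a stronger reading that a reader might infer: that a responder who dies during survival follow-up would be recoded, so the ORR could keep changing for years. Patients off treatment "will still be followed clinically for toxicity and survival endpoints" (Section 13.1), and Section 9.1 runs survival follow-up for at least two years after the last dose, so the reading is possible. The documents do not establish it. *The study* is undefined, Section 13.1 is headed as removal from study but lists reasons for stopping treatment, and Sections 12.0 and 14.0 tie the endpoint to six months. The clear conflict is therefore a death inside the window.

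*Responses are counted as they occur.* Section 14.0 lets enrolment pass the 16th patient once three radiographic responses have been seen, which argues against recoding at stage 1. That is fair, but recoding only at the final analysis gives nearly the same power (0.743, 0.675 and 0.514).

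*The effect is conservative.* This also stands: the rule can only lower the ORR and cannot create a false claim of activity. Missing an active regimen is, however, the error that the stated power of 0.8 is meant to limit.

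**Conclusion.** The sentence is wrong as written and should be corrected. It contradicts the ORR definition, the decision rule and, for a response that meets the Section 12.0 criteria, best overall response. The clearest case is a documented responder who dies within six months of Cycle 1 Day 1.

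The direction is certain: a lower ORR, lower power and lower type I error. The size is conditional. Power at a true ORR of 35% goes from 0.801 to 0.740, 0.670 or 0.507 if 5%, 10% or 20% of responders are recoded at both stages. A reader might infer from these figures that the trial is underpowered as it stands. The documents do not support that: they give no share of responders who die in any window, and under the likely intent the share recoded is zero and the stated design holds. The finding is a contradiction in the primary-endpoint count, not evidence that responders will in fact be removed.

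**What to change.** Replace the coding sentence in Section 14.0 with:

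> Patients who die or are not evaluable (including no CT evaluation) without a previously documented CR or PR, as defined for the primary endpoint, within 6 months of C1D1 are counted as non-responders; a response documented in that window is kept regardless of later death, which is counted in PFS and OS.

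This keeps the all-patients denominator and the conservative handling of missing scans. It deliberately does not settle whether a response must be confirmed. Section 12.0 refers to confirmation criteria, while the ORR definition in Section 14.0 accepts CR or PR at any reassessment. A PR at the first scan followed by death turns on that difference, which should be reconciled separately.

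The cost is one sentence. Sample size, stage 1 and final cut-offs, and trial conduct do not change.

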Follow-up Period: Patients will be followed for survival every 3 months at routine clinic visits or via phone call if they are no longer being seen at MSKCC or JHU for a minimum of 2 years after the last dose of study drug treatment.

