³ Urinalysis will include assessments of turbidity and color, pH, specific gravity, protein, ketones, bilirubin, occult blood, nitrite, glucose, and leukocyte esterase. Urine microscopic analysis will include erythrocytes, leukocytes, bacteria, casts, and crystals.

⁴ CT scans and brain MRIs will be obtained at the completion of every 2 cycles (approximately every six weeks).

⁵ CTCs for PDX engrafting will only be collected from samples from patient's treatment at MSKCC main campus. Due to feasibility barriers with transporting samples, no patient samples from MSKCC Regional Care Centers or from JHU will be collected for this purpose. Each sample will include two 10 cc EDTA tubes to be transported on ice.

⁶ CTCs for analysis by EPIC Sciences will be collected from all MSKCC sites and all JHU sites. Each sample will include one 10 cc Streck tube to be transported at room temperature.

⁷ CTCs for banking at MSKCC will be collected from all MSKCC sites and all JHU sites. Each sample will include one 10 cc Streck tube to be transported at room temperature.

⁸ Any fresh tissue biopsy will be performed ONLY if deemed medically safe by the institutional PI. There will be a window of +/- 4 days for the biopsy. The pre-treatment tissue sample can be archival if there is adequate tissue.

⁹ Post-progression tissue biopsy is OPTIONAL.

¹⁰ PK draws: There is a \pm 15-minute window for PK blood draws. PK assessments will be obtained in both Phase I and Phase II. Please see Table 4 for the complete PK schedule. Each PK blood draw will include 5 cc of blood collection.

Table 4.0 Pharmacokinetics (PK) Schedule for DS-3201b (Phase I and Phase II)

Cycle and Day	Time point						
7 days prior to C1D1	0.5-hour post-dose	1-hour post-dose	2-hour post-dose	4-hour post-dose	6-hour post-dose	8-hour post-dose	
Cycle 1 Day 1	Pre-dose	0.5-hour post-dose	1-hour post-dose	2-hour post-dose	4-hour post-dose	6-hour post-dose	8-hour post-dose
Cycle 1 Day 8	Pre-dose						
Cycle 1 Day 15	Pre-dose	0.5-hour post-dose	1-hour post-dose	2-hour post-dose	4-hour post-dose	6-hour post-dose	8-hour post-dose
Cycle 2 Day 1	Pre-dose						

Correlative Studies:

Studies Using Tumor Tissue:

We will obtain mandatory on-treatment core biopsies at Cycle 3 Day 1 +/- 4 days. The Cycle 3 Day 1 biopsy may be canceled if deemed medically unsafe (e.g., prior biopsy resulting in pneumothorax or other complication, bleeding diathesis, etc.) by the PI. The end of trial (EOT) biopsy will be optional.

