12.0 CRITERIA FOR THERAPEUTIC RESPONSE/OUTCOME ASSESSMENT

Determining the Safety, Tolerability, MTD and RP2D of DS-3201b in Combination with Irinotecan

The Common Terminology Criteria for Adverse Events (CTCAE) 5.0 will be used to determine all adverse events and dose-limiting toxicities.

Determining the Objective Response Rate (ORR) to Treatment with DS-3201b at the RP2D in Combination with Irinotecan

The Response Evaluation Criteria in Solid Tumors Group (RECIST v1.1) criteria will be used to evaluate the response to treatment.²⁹

Target Lesions

Change in disease will be assessed by repeat chest/abdomen/pelvis CTs at baseline and at every other cycle thereafter.

Complete Response (CR): Complete absence of all signs of disease without any new lesions or disease-related symptoms.

Partial Response (PR): A reduction of $\geq 30\%$ as compared to the baseline measurement.

Stable disease (SD): Neither sufficient shrinkage to qualify for PR nor sufficient increase to qualify for PD taking as references the smallest sum the longest diameter (LD) since the treatment started.

Progressive Disease (PD): An increase of $\geq 20\%$ over the nadir measurement is defined as progressive disease.

Non-Target Lesions

All other lesions (or sites of disease) not included in the "target lesions," including small lesions (longest diameter < 20 mm with conventional techniques or < 10 mm with spiral CT scan) and truly non-measurable lesions, should be identified as non-target lesions and recorded at baseline. Measurements are not required, and these lesions should be followed as defined below.

Lesions that are considered non-measurable include bone lesions, leptomeningeal disease, ascites, pleural/pericardial effusion, abdominal masses that are not confirmed and followed by imaging techniques, and cystic lesions.

Complete response: Disappearance of all non-target lesions.

Non-complete response/Non-progression: Persistence of one or more non-target lesions.

Progression: Appearance of one or more new lesions. Unequivocal progression of existing non-target lesions.

Evaluation of Best Overall Response

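### No tumor imaging is scheduled after treatment stops, while death at any later time counts as a PFS event, so a patient who stops without progression and later dies can have PFS equal to survival

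*Combined protocol and SAP*

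**What the plan says.** **Imaging.** Footnote 4 to Table 3.0 (Section 10.1) states: "CT scans and brain MRIs will be obtained at the completion of every 2 cycles", roughly six-weekly. Section 12.0 agrees: "Change in disease will be assessed by repeat chest/abdomen/pelvis CTs at baseline and at every other cycle thereafter". In Table 3.0 the CT and MRI rows are marked at baseline and from Cycle 3 on; their end-of-treatment cells are blank.

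**After treatment.** Section 13.1: "Withdrawal procedures will include an end-of-treatment (EOT) visit within 30 days of the last dose of study drug", with no scan attached. The follow-up paragraph of Section 9.1: "Patients will be followed for survival every 3 months at routine clinic visits or via phone call", for at least 2 years. Section 13.1 adds that patients off study drug "will still be followed clinically for toxicity and survival endpoints, unless the patient explicitly declines".

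**Stopping without progression.** Section 13.1 lists adverse events, investigator judgment, non-compliance and withdrawal as reasons apart from progression. Tables 5.0 and 6.0 and Section 11.6 also contain toxicity rules that end treatment. No expected stopping rate is given.

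**Endpoints.** In Section 14.0 PFS ends at documented progression or at death from any cause, and is otherwise "censored on the date of last tumor assessment". Section 12.0 ends duration of response at objectively documented recurrence or progression. It does not mention death, and no censoring rule is given there or in Section 14.0.

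**The concern.** PFS depends on looking for progression on the same footing in everyone until it occurs. Here the scheduled looking ends with treatment, but the clock can run on until death. In recurrent small cell lung cancer, with at least 2 years of survival follow-up, many patients who stop early will die under observation. For those with no progression documented in between, the time from unseen progression to death is added to PFS.

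PFS and duration of response are named secondary objectives. The trial has one arm, so no control group shares the error, and it passes directly into any comparison with outside data. Phase II has at most 31 patients, so a few such cases can be seen in the curve.

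**Working it through.** **No figure to reproduce.** The plan states no assumed PFS, event count or power for PFS. Its one powered calculation, the Simon design (2 or fewer responses in 16 stops; 9 or more in 31 succeeds; 16% against 35%), reproduces by exact binomial: early stopping 0.516 (stated 52%), type I error 0.047 (limit 0.05), power 0.801 (target 0.80). This point does not touch it.

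**Inputs.** From the plan: scans every 6 weeks (42/30.44 = 1.38 months, so at 1.38, 2.76, 4.14 and 5.52 months) and death as a PFS event without a time limit. Assumed: exponential times; median time to progression *m* = 3 to 4.5 months; median post-progression survival *p* = 3 to 4 months; a share *f* = 10, 20 or 30% stopping before progression; stopping unrelated to prognosis.

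**Excess in 6-month PFS when PFS runs to death.** The last scan before month 6 is at T = 5.52. The excess is the probability of having stopped first, progressed by T, and still being alive at month 6:

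Excess = ∫₀ᵀ λe^(−λt) · (1 − e^(−σt)) · e^(−μ(6−t)) dt, with λ = ln2/m, μ = ln2/p, σ = λf/(1−f).

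Example: m = p = 3, f = 30%. Then λ = μ = 0.2310, σ = 0.0990 and e^(−6λ) = 0.25. Because λ = μ, the integral is λe^(−6λ) · [T − (1 − e^(−σT))/σ] = 0.2310 × 0.25 × (5.520 − 4.252) = 0.073. Simulation of 400,000 patients gives the same: 0.351 against 0.278 with continued scanning.

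Excess in percentage points, if no stopper has progression documented:

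| m, p (months) | f = 10% | f = 20% | f = 30% |
|---|---|---|---|
| 3, 3 | 2.2 | 4.6 | 7.3 |
| 3, 4 | 2.5 | 5.3 | 8.4 |
| 4, 3 | 1.5 | 3.3 | 5.3 |
| 4, 4 | 1.7 | 3.7 | 6.1 |
| 4.5, 3 | 1.3 | 2.8 | 4.6 |
| 4.5, 4 | 1.5 | 3.2 | 5.2 |

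If a random half of stoppers have progression documented on the same six-weekly timing, each entry halves, to about 0.6 to 4.2 points.

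**Median.** Progression can be dated only at scans, so the estimated median tends to sit on a scan date. Just after the 4.14-month scan, true PFS is 2^(−4.14/m): 0.384 for m = 3, 0.441 for 3.5, 0.488 for 4 and 0.529 for 4.5. Only m = 4 lies close enough to 0.5 for a small bias to push the median towards the next scan (4.1 to about 5.2–5.5 months at 20–30% stopping). For m = 3, 3.5 and 4.5 it is essentially unchanged.

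**Censoring at the last on-treatment scan instead.** Simulated 6-month PFS for m = 3, p = 3, f = 30%, by progression hazard after stopping relative to before:

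| Hazard ratio | Continued scanning | Censored at last scan | Difference (points) |
|---|---|---|---|
| 0.7 | 0.304 | 0.253 | −5.1 |
| 1 | 0.278 | 0.256 | −2.2 |
| 2 | 0.223 | 0.256 | +3.3 |

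Over a wider set (m = 2 to 4) the range is about −6 to +3 points. The sign depends on a hazard that the documents do not give.

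**Duration of response.** Death is not an event in Section 12.0, so the run-to-death calculation does not apply. What is left is missed progression under an unstated censoring rule, again with no determined sign.

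**The case against.** The best case against the point is that the plan is not silent.

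- Section 13.1 gives Phase II patients who stop before two cycles, but have completed the DLT period, the first repeat CT.
- Section 12.0 asks for every effort to document progression after discontinuation.
- Section 14.0 says absence of progression will be documented in living patients before data cutoff, dropout or new anticancer treatment.
- Section 17.1 lists time to progression among the data collected, and the PFS definition is not limited to protocol scans.

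Some of this stands. Follow-up is not for survival alone, and the figures that assume no stopper ever has progression documented are a worst case. But the first item is one early scan, the second belongs to the paragraph on symptomatic deterioration and has no schedule, and the third sets neither a scan nor a clear censoring rule. None limits the gap between the last scan and a death counted as an event.

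The consequence is also modest. PFS has no hypothesis or decision rule. With 31 patients and 6-month PFS near 38%, the 95% half-width is 1.96 × √(0.38 × 0.62/31) = 17 points, larger than any bias above. That argues for a cheap remedy. It does not argue for none, because bias adds to sampling error and the interval does not show it.

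A reader might infer that early censoring also favours the regimen, that duration of response is overstated, or that median PFS is inflated by more than a month. The documents support none of these. The first has no fixed sign, the second has no death event through which to run on, and the third depends on a true median close to 4 months.

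**Conclusion.** The gap is real, and one direction of bias is established. Where PFS runs on to a death that follows unobserved progression, PFS is overstated: by about 1 to 8 points at 6 months if no stopper has progression documented, and half that if half do. These sizes rest on assumed progression, survival and stopping rates. The median is often unaffected. For patients censored at the last scan, and for duration of response, the defect is missing information and incomplete rules, with uncertain direction.

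The primary analysis is essentially unaffected, since Section 14.0 counts unevaluable patients as non-responders and the Simon figures reproduce. This is a worthwhile low-cost improvement to secondary endpoints and does not put the trial's main conclusion at risk.

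**What to change.** 1. **Follow-up data.** At each existing 3-monthly contact, also record the date of any progression on usual-care imaging and the start date of the next anticancer treatment. Use that progression date as the event for PFS and for duration of response.
2. **Section 14.0 rules.** State how death and new anticancer treatment are handled for PFS and, separately, for duration of response.
3. **Sensitivity analysis.** Censor PFS at the last scan when death occurs more than a stated time after it (for example 12 weeks, two 6-week scan intervals) or after new anticancer treatment. Elapsed time is needed because, with no scans scheduled off treatment, a rule based on missed assessments cannot operate. Which rule should be primary is open to debate, and early censoring carries its own bias, so showing both is the safer course.

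The cost is two eCRF fields and a short addition to Section 14.0, with no extra scans and no change to treatment. The drawback is that usual-care scans are irregularly timed, so some progression dates will be late or missing. The report should say how many patients stopped without progression and how many of them later had a progression date.
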